In the ITT analysis, individuals were assigned to the study arm to which they were randomized. Thus,  $Intervention_i$  is equal to 1 if participant  $i$  is randomized to the intervention arm and 0 otherwise.  $Time_t$  is a continuous measure of time capturing differences in months between assessment  $t$  and assessment  $t - 1$ . Because the intervention ended by the time of the 6-month assessment, we centered the time variable at 6-month follow-up in the following way:  $Time_t$  equals to -4 for 2-month follow-up, 0 for 6-month follow up, and 6 for 12-month follow-up. To model the pattern of outcome changes over time, our primary analysis employed linear spline models to divide the time axis into two segments, and within each segment consider piecewise linear trends (e.g., having a different time trend before and after the intervention ended). Specially, we denote  $t^*$  to be the month when the intervention stopped, i.e., 6 months after baseline and  $(Time_t - t^*)_+$  to be the post-intervention time trend, which equals to  $(Time_t - t^*)$  if  $Time_t > t^*$  and 0 otherwise. This choice of linear spline models allows for the ability to test whether the time trends differ before and after the intervention was finished and that treatment effect could attenuate over time once participants do not receive more intervention.

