Since the time variable is centered at 6-month follow-up, the beta coefficient on  $Intervention_i$  can be interpreted as the treatment effect on outcome levels evaluated at the end of the intervention. That is, testing for the significance of  $\beta_1$  tests the hypothesis that the treatment was more effective than enhanced usual care in improving the outcomes, as evaluated at 6 months after the baseline. The coefficient of intervention by time interaction  $\beta_3$ , tests whether the pattern of outcomes over time would be no different between treatment and enhanced usual care groups. Similarly,  $\beta_5$  tests whether changes in outcome responses over time were different between treatment and control groups after the intervention had ended. The constant term  $(\alpha_{00} + \gamma_{00})$  in equation (1) represents the level of the outcome variables in the absence of the intervention ( $Intervention_i = 0$ ) at 6-month follow-up ( $Time_t = 0$  and  $(Time_t - t^*) = 0$ ). The term  $\omega_{0i}$  denotes the participant-specific random effect,  $\epsilon_{0j}$  the site-specific random effect, and  $\varepsilon_{itj}$  denotes the

residual error term.  $X_i$  includes the baseline measure of the outcomes to control for severity of the outcome at baseline. We also estimated the effect of the intervention six months after it ended, i.e., 12-months after baseline, using the time-by-intervention interactions. Given  $Time_t = 6$  for the 12-month follow-up and  $t^* = 6$  since PMSB lasted six months, the intervention effect evaluated 12 months after baseline is given by  $\beta_1 + \beta_2 \times 6 + \beta_3 \times 6$ .

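### The interaction coefficients of the spline model are misdescribed: β3 covers only months 2–6 and β5 is a change in slope difference, so neither alone tests the overall pattern or fading after month 6

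*Combined protocol and SAP*

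**What the plan says.** All of this is in the Combined protocol and SAP, Analytical methods, in the text around equation (1).

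- **Model.** The plan states that "our primary analysis employed linear spline models to divide the time axis into two segments" and will "within each segment consider piecewise linear trends".
- **Time scale.** Time is centred at month 6. The visit values, the first of which carries a minus sign in the plan, are "4 for 2-month follow-up, 0 for 6-month follow up, and 6 for 12-month follow-up".
- **Knot.** t* is defined as "to be the month when the intervention stopped, i.e., 6 months after baseline". The later text also sets t* equal to 6.
- **Purpose.** One reason given for the spline is that the "treatment effect could attenuate over time once participants do not receive more intervention".
- **β3.** It "tests whether the pattern of outcomes over time would be no different between treatment and enhanced usual care groups". The sentence is not limited to months 2–6.
- **β5.** The next sentence says that it "tests whether changes in outcome responses over time were different between treatment and control groups after the intervention had ended".
- **Other looks at month 12.** "We also estimated the effect of the intervention six months after it ended", and sensitivity model (3) uses visit indicators with separate 6- and 12-month effects.

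No joint test of β3 and β5 is described. The only joint test in the plan is the one across the five outcomes, on the β1 terms.

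**The concern.** In a two-segment spline the coefficient on time describes the first segment, and the coefficient on the spline term describes how the slope changes at the knot. The plan reads the first as a test of the whole pattern and the second as a test of what happens after the knot. If both are mislabelled, a reader who follows the plan's interpretation could draw the wrong conclusion about whether benefit persists once the sessions stop, which is the question the spline was chosen to address.

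**Working it through.** **Inputs from the plan:** Time = −4, 0, 6; two arms; spline term equal to (Time − knot) when positive and 0 otherwise; 307 participants; 70 excluded from the physical-function analyses, leaving 307 − 70 = 237.

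**Assumed, because the plan does not give them:** two-sided 5% level, equal arms, outcome SD of 1 at each visit, between-visit correlation ρ = 0.65, complete data, and no allowance for site clustering or imputation. The correlation with baseline, if the same at every visit, cancels out of every contrast below.

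**1. Where the knot is.** With the knot at 0 on the centred scale, the spline column is 0, 0, 6 and all six arm-by-time coefficients are estimable. With t* = 6 used literally on that scale, the column is 0, 0, 0. β4 and β5 then cannot be estimated, and β3 becomes one slope difference across months 2–12. The rest of this check uses the knot at 0, the only reading under which the model has two segments.

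**2. What the coefficients are.** Let D2, D6 and D12 be the arm differences at the three visits.

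- β1 = D6
- β3 = (D6 − D2)/4
- β3 + β5 = (D12 − D6)/6
- β5 = (D12 − D6)/6 − (D6 − D2)/4

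β3 contains no month-12 data. Equal patterns require D2 = D6 = D12, that is, β3 = 0 and β5 = 0 together.

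**3. Illustrative patterns (arm differences assumed).**

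| D2 / D6 / D12 | β3 | β5 | β3 + β5 |
|---|---|---|---|
| 1 / 1 / 0 (complete fade) | 0 | −0.167 | −0.167 |
| 0.5 / 1 / 1 (growth, then plateau) | 0.125 | −0.125 | 0 |
| 0.2 / 0.6 / 1.2 (steady divergence) | 0.1 | 0 | 0.1 |

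Row 1: β3 misses the fade. Row 2: β5 is non-zero although the arm difference does not change after month 6. Row 3: β5 is zero although the arms keep diverging after month 6.

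**4. Rejection rates for a complete fade: D = −0.30, −0.30, 0 SD.** The variance of a contrast with weights c on (D2, D6, D12) is (4/N)(1 − ρ)Σc². Here (4/307) × 0.35 = 0.00456.

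| Test | Value | Σc² | SE | z | Rejects |
|---|---|---|---|---|---|
| β3 | 0 | 0.125 | 0.0239 | 0 | 5% |
| β5 | 0.05 | 0.2639 | 0.0347 | 1.44 | 30% |
| β3 + β5 | 0.05 | 0.0556 | 0.0159 | 3.14 | 88% |

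For the joint 2-df test, the non-centrality is Σ(D − mean D)²/0.00456 = (0.01 + 0.01 + 0.04)/0.00456 = 13.2, which gives 91%.

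The SE of β5 is √(0.2639/0.0556) = 2.18 times that of β3 + β5, whatever N and ρ are, because β5 also carries the noise of the month 2–6 slope.

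**5. Range.** For ρ from 0.5 to 0.8 with N = 307, β5 rejects 23% to 48% of the time and the joint test 78% to 99%. With N = 237 and ρ = 0.65 the figures are 24% and 82%.

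**The case against.** A reader might infer that the plan judges the pattern from β3 alone and would report a fading benefit as no difference. The documents do not support that. The sentence after the β3 statement turns to the period after the intervention and assigns it to β5, which is non-zero in the fade scenario. A 12-month effect is planned, and model (3) would show about −0.30 SD at month 6 and 0 at month 12 in that scenario, given no difference at baseline. No text says that fading is judged from β3. So 5% against 91% compares one coefficient with the best test and does not describe the whole plan. The scenario also makes β3 exactly zero, and its effect sizes and correlation are assumptions.

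It can further be argued that the β3 sentence merely omits a restriction to the first segment, that separate interaction tests are legitimate, and that with t* = 6 taken literally β3 does use month 12.

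Most of this stands, and it limits the consequence. It does not reduce the point to wording. β5 does not have the meaning the plan gives it, and as a test of a complete fade it is far weaker than β3 + β5. The literal t* = 6 is no defence, because it removes the second segment. Model (3) is a sensitivity analysis with no stated test of the 6- against the 12-month effect. The 12-month effect is printed as β1 + 6β2 + 6β3, which includes the control-arm trend and omits β5; with the knot at 0 it should be β1 + 6β3 + 6β5. That is a separate error and is not needed for this point, but it means the printed formula cannot be relied on to show a fade.

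**Conclusion.** The point holds in limited form. With the knot at month 6, the plan misstates what β3 and β5 test: neither alone tests the pattern over the whole follow-up, and β5 is not the post-intervention slope difference. In the assumed complete-fade scenario, the two coefficient tests that the plan describes reject about 5% (β3) and 30% (β5) of the time, against 88% for β3 + β5 and 91% for the joint test. The algebra depends only on the visit coding and the knot. The percentages depend on the assumptions listed and would change with dropout, clustering and the true correlation.

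The documents do not show that a fade would be missed or reported as no difference. With the knot at 0, the 6-month effect β1 is D6 and is unaffected. The matter should be corrected because it concerns the stated purpose of the spline, but it does not undermine the 6-month comparison.

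**What to change.** 1. State the knot as 0 on the centred time scale, and print the spline term in equations (1) and (2) with its positive-part definition.
2. Test the overall pattern for each outcome with the joint 2-df hypothesis β3 = β5 = 0.
3. Describe and report β3 as the month 2–6 slope difference.
4. Test and report β3 + β5, with its confidence interval, as the month 6–12 slope difference. Describe β5 as the change in slope difference at month 6.

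The cost is one Wald test and one linear contrast per outcome, pooled over the 20 imputed datasets, and a few sentences of text. No new data are needed. If the analyses were already run with the knot at 0, both results come from the existing fits. If t* = 6 was used literally on the centred scale, the models must be refitted.

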Although missing a follow-up assessment did not seem to be related to participants’ demographic characteristics, to account for missing data we used multiple imputation methods in Stata version 15.1 via the *mi impute chained* command (5). Multiple imputation was carried out in three steps. First, we imputed the missing data for all the variables considered, creating 20 imputed datasets each one consisting of 307 participants with three follow-up assessments per participant. In the second step we ran analysis on each individually imputed data set. Finally, we aggregated the individual estimates to obtain final estimates and adjusted standard errors for the uncertainty due to imputation (6).

Each imputation was carried out using the chained equations method (7). In what follows, we refer to variables with missing data as incomplete variables and those with non-missing data as complete variables. Each incomplete variable  $x_j$  was specified as a conditional function ( $g_j$ ) given the set of all other variables used in the imputation, comprising both incomplete ( $x_1, \dots, x_m$ ) and complete variables ( $Z$ ). We fitted the conditional model  $g_j$  to generate the predicted values of  $x_j$  using an iterative method. Specifically, each incomplete variable  $x_j$  was iteratively estimated and in each iteration the variable  $x_j^t$  was then updated to  $x_j^{t+1}$  based on the conditional model. This updated variable was then used in the estimations of the other variables, following the conditional model specification

$$x_j^{t+1} \sim g_j(x_j \mid x_1^{t+1}, \dots, x_{j-1}^{t+1}, x_{j+1}^t, \dots, Z, \phi_j),$$

for  $j \in \{1 \dots m\}$ , where  $\phi_j$  were parameters of the conditional model  $g_j$ . These steps were repeated for all variables  $x_1, \dots, x_m$  and, after an initial burn-in phase, the procedure was stopped once convergence was reached.

The variables used for imputation included main outcome variables and their baseline measures, participant socio-demographics, clinical characteristics, and study design variables, such as site and intervention indicators, as well as dummy indicators for each follow-up assessment.

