We used interval regressions to incorporate the theoretical bounds of the clinical outcome variables to increase the efficiency and accuracy of the imputation procedure (e.g., we restricted the imputed values of PHQ-9 to lie within the 0 to 27 intervals). We used logistic regression models to impute binary variables, and linear regression models to impute continuous variables.

For Analysis, first, we compared distributions of baseline characteristics between participants who received the PMSB intervention and participants in the usual care group, to assess the balance of the observed covariates. For each follow-up assessment, we compared the baseline covariates to detect any significant baseline differences between those who completed assessment versus those who did not.

Second, to assess the effect of the intervention, we conducted an intent-to-treat (ITT) analysis, using a multilevel, multivariate regression model to assess changes in outcome variables over time in the treatment and control groups. To account for the nature of longitudinal data, the ITT analysis was carried out by fitting multilevel mixed-effects models to allow for valid variance calculation and statistical inference. The multilevel models computed included random effects at both participant- and site-level to account for within-participant and within-site correlations, as well as robust clustered standard errors to account for within-site correlations due to participants nesting within same site. Letting  $Y_{itj}$  denote the outcome measured at time  $t$  after the baseline for participant  $i$  at site  $j$ , we estimated the following model:

$$(1) \quad Y_{itj} = \beta_{0i} + \beta_{0j} + \beta_1 Intervention_i + \beta_2 Time_t + \beta_3 Intervention_i \times Time_t + \beta_4 (Time_t - t^*) + \beta_5 Intervention_i \times (Time_t - t^*) + \beta_6 X_i + \varepsilon_{itj}$$

where the participant-specific random intercept can be written as  $(\beta_{0i} = \alpha_{00} + \omega_{0i})$  and the site-specific random intercept can be written as  $(\beta_{0j} = \gamma_{00} + \epsilon_{0j})$ . We fitted only linear models as all our outcomes were continuous.

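### A single time-constant baseline coefficient leaves the time-pattern tests unadjusted and gives the 12-month effect an averaged slope: a small, recoverable loss of precision

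*Combined protocol and SAP*

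**What the plan says.** All references are to the Analytical methods section of the combined protocol and SAP.

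- **Purpose of the model.** It is fitted "to assess changes in outcome variables over time in the treatment and control groups". X_i "includes the baseline measure of the outcomes to control for severity of the outcome at baseline".
- **Form of the baseline term.** Equation (1) contains β6·X_i and no product of X_i with Time or with the spline term. Equation (2) lets the coefficient differ by outcome (β6h) but not by visit.
- **Random effects.** The model has "random effects at both participant- and site-level to account for within-participant and within-site correlations". The equation shows these as intercepts, with no random slope.
- **Data analysed.** Imputation is described as "creating 20 imputed datasets each one consisting of 307 participants with three follow-up assessments per participant". The imputation variables include baseline measures "as well as dummy indicators for each follow-up assessment", with no baseline-by-visit interaction stated.
- **Time coding.** Time "equals to -4 for 2-month follow-up, 0 for 6-month follow up, and 6 for 12-month follow-up", and t* is given as 6.
- **Tests.** β1 is the effect at month 6. β3 "tests whether the pattern of outcomes over time would be no different between treatment and enhanced usual care groups". β5 is read as the arm difference in change after the intervention ended. A combination of coefficients gives the 12-month effect.

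**The concern.** A baseline covariate with one coefficient for all visits shifts a participant's three fitted values by the same amount. It can adjust the level of the outcome but not its change. The spline was chosen to show whether the effect attenuates after the intervention ends, and the collected baseline score contributes nothing to that question.

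A baseline score may predict an early visit better than a late one. If so, the common slope is too steep at month 12. The 12-month effect is then over-corrected for any chance baseline difference, and both that effect and the change contrasts are less precise than the data allow.

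No other planned analysis fills the gap. Equation (3) has no X_i, and its contrast β33 − β32 is the same unadjusted 6-to-12-month change. The service-use, severity, race/ethnicity, language and site analyses test interactions with intervention, not time.

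**Working it through.** **Inputs from the documents.** 307 participants with three visits each; times −4, 0, 6; blocks of two, so about 1:1 allocation; 307 − 70 = 237 for physical function outcomes. The plan prints no correlation, SD or power figure, so there is no design figure to reproduce.

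**Assumptions.** Outcome SD 1 at each visit; baseline-outcome correlations b2/b6/b12 as tabulated; correlation 0.62 between every pair of follow-up visits; knot at centred time 0, where equation (1) gives a 12-month effect of β1 + 6β3 + 6β5.

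**Step 1: cancellation.** With that knot, β3 = (D6 − D2)/4 and β5 = (D12 − D6)/6 − (D6 − D2)/4, where Dt is the arm difference at month t. A term constant over visits drops out of both. Fits to one simulated set of 307 × 3 rows gave β3 = 0.00726 (SE 0.02549) and β5 = −0.03413 (SE 0.03704), identical with and without X_i. These fits used model-based standard errors; the plan's robust standard errors would not alter the point estimates.

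**Step 2: averaged slope.** On balanced data the effect at visit t is Dt − b̄·DX, where DX is the baseline arm difference and b̄ = (b2 + b6 + b12)/3. Using the visit's own slope would give Dt − bt·DX.

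**Step 3: variance penalties.**
- Effect at visit t: (b̄ − bt)² / (1 − bt²).
- Change between two visits: d² / [2(1 − 0.62) − d²] = d² / (0.76 − d²), where d is the difference between the two slopes.

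| b2/b6/b12 | 12-month effect | β3, and 6-to-12-month change |
|---|---|---|
| 0.5/0.5/0.5 | 0 | 0 |
| 0.6/0.5/0.4 | 0.01/0.84 = 1.2% | 0.01/0.75 = 1.3% |
| 0.65/0.5/0.35 | 0.0225/0.8775 = 2.6% | 0.0225/0.7375 = 3.1% |
| 0.7/0.5/0.3 | 0.04/0.91 = 4.4% | 0.04/0.72 = 5.6% |

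β3 and the 6-to-12-month change share a column because the correlations fall by equal steps. At month 6, b̄ = b6, so the penalty is zero. The percentages do not depend on N. The last row is worth about 307 × 0.044/1.044 = 13 participants at month 12.

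β5 is the difference of two slopes, so a steady decline in correlation largely cancels. For 0.7/0.5/0.3 the baseline component is −0.2/6 + 0.2/4 = 0.0167. The unadjusted variance factor is 0.38 × (0.0625 + 0.1736 + 0.0278) = 0.1003. The penalty is 0.00028/(0.1003 − 0.00028) = 0.3%.

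**Step 4: conditional shift at month 12.** This is (b12 − b̄)·DX. One standard error of DX is 2/√307 = 0.114 SD. The shift is then 0.1 × 0.114 = 0.011 SD to 0.2 × 0.114 = 0.023 SD in size, or about 0.1 to 0.2 of a 12-month standard error of 0.105 to 0.109 SD. The conditional two-sided error becomes 5.1% to 5.5%. An imbalance of 0.2 SD (1.75 SE, two-sided probability about 8%) gives 5.4% to 6.6%.

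**Step 5: simulation.** With 8,000 trials per setting at N = 307 and 237, and 0.7 between adjacent follow-ups, visit-specific slopes cut the 12-month variance by 4% to 5% for 0.8/0.6/0.4 and about 1% for 0.7/0.6/0.5. With flat slopes (0.6/0.6/0.6) that variance hardly changed, and the variance of the 6-to-12-month change rose by 0.4% to 0.5%. Simulated means lay within about 0.003 of zero under every version.

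**The case against.** A constant baseline slope is a standard specification, and the plan never claims that baseline adjustment sharpens β3 or β5. Those are within-person contrasts, from which stable differences between participants are already removed. β1, the test of effectiveness at the end of the intervention, gains essentially nothing. All of this stands.

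A reader might infer that the time-pattern tests are invalid, or that regression to the mean will look like a fading effect. The documents do not support that. Equation (1) has no baseline row among its outcomes, so a chance imbalance reaches the change contrasts only if the baseline slope differs between months 2, 6 and 12, and no figure shows that it does. Averaged over randomisation, the estimates are unbiased and the error rate is not inflated. The higher conditional error needs an uncommon imbalance together with falling correlations.

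One reservation remains. For SPPB, LLFDI and WHODAS 2.0, 35 intervention participants and their 35 block counterparts were excluded for reasons that include events after randomisation. Balance in the remaining 237 no longer rests on randomisation alone. The plan says that balance was confirmed but gives no figures, so this neither shows an imbalance nor rules one out.

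A reader might also take the repair to be free. It is not: the imputation needs matching terms, and the spline coding must be repaired first. That coding is a separate defect, with more effect on β5 and the 12-month estimate than this point has.

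**Conclusion.** The structural point holds: as specified, baseline adjustment has no effect on β3, β5 or the 6-to-12-month change, and the 12-month effect uses an averaged slope. The exact cancellation relies on random intercepts and completed three-visit data, both of which the plan states. With 20% of later visits missing and left unimputed, simulated β3 moved only from −0.00373 to −0.00284 when X_i was added.

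This is an optional refinement, not an error that undermines the analysis. The size rests wholly on assumed correlations: nothing if slopes are flat, and otherwise the low single-digit percentages tabulated above, with β5 itself hardly affected when the correlation declines steadily.

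**What to change.** 1. **Repair the knot first.** With time coded −4/0/6 and t* = 6, (Time − t*)+ is zero at every visit, so any product with it is a column of zeros. Without the plus sign, as equation (1) prints it, the term is collinear with Time. The plan's own reading, in which the spline term is zero at month 6, points to a knot at centred time 0. Restate the 12-month effect as β1 + 6β3 + 6β5; the printed formula includes β2 and omits β5.
2. **Add baseline-by-time terms.** Centre X_i at the overall mean. Add X_i × Time and X_i × (Time)+ to equation (1), which is equivalent to baseline-by-visit terms, and the outcome-specific versions to equation (2).
3. **Match the imputation.** Let the baseline slope differ by visit there too. If the imputation was run in long form without such terms, imputed values would pull the visit slopes towards their average.
4. **Label it.** The analysis is reported as done, so present the result as a sensitivity analysis beside the current one.

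The cost is re-running the imputation and models, two more coefficients per outcome (ten in equation (2)), and up to about 0.5% more variance if slopes are flat. No new data are needed.

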$$(2) \quad Y_{hitj} = \beta_{0hi}Outcome_h + \beta_{0hj}Outcome_h + \beta_{1h}Intervention_i \times Outcome_h \\ + \beta_{2h}Time_t \times Outcome_h + \beta_{3h}Intervention_i \times Time_t \times Outcome_h \\ + \beta_{4h}(Time_t - t^*) \times Outcome_h + \beta_{5h}Intervention_i \times (Time_t - t^*) \times Outcome_h \\ + \beta_{6h}X_i \times Outcome_h + \varepsilon_{hitj}Outcome_h$$

where  $h = 1$  for SPPB,  $h = 2$  for LLFDI,  $h = 3$  for WHODAS 2.0,  $h = 4$  for HSCL-25, and  $h = 5$  for GAD-7. Since the time variable is centered at 6-month follow-up, the beta coefficients on  $Intervention_i \times Outcome_h$ ,  $\beta_{1h}$ , can be interpreted as the treatment effect on outcome  $h$  evaluated at the end of the intervention. After modeling the outcomes jointly, we conducted a joint global test to evaluate the null hypothesis that all treatment effects were zero, i.e.,  $\beta_{11} = \beta_{12} = \beta_{13} = \beta_{14} = \beta_{15} = 0$ . This joint test considers the correlation among measures, which is likely to be different from zero in our context, e.g., participants with low SPPB scores are likely to also self-report lower LLFDI scores.

Second, we examined whether our intent-to-treat results were robust to more traditional models that included only an indicator for intervention, three indicators of time (2-, 6- and 12-months) and their two-way interactions using the following model:

$$(3) \quad Y_{itj} = \beta_{0i} + \beta_{0j} + \beta_1Intervention_i + \beta_{21}Time_1 + \beta_{22}Time_2 + \beta_{23}Time_3 \\ + \beta_{31}Intervention_i \times Time_1 + \beta_{32}Intervention_i \times Time_2 \\ + \beta_{33}Intervention_i \times Time_3 + \varepsilon_{itj}$$

where  $Y_{itj}$  denotes the outcome measured at baseline, 2-, 6- and 12-months ( $t = 0, 1, 2,$  and  $3,$  respectively) for participant  $i$  at site  $j$ ,  $Time_1, Time_2, Time_3$  are indicator variables for the 2-, 6- and 12-month follow-ups, respectively (baseline is the reference period), and  $Intervention_i \times Time_1, Intervention_i \times Time_2, Intervention_i \times Time_3$  are the two-way interactions between the intervention indicator and the time indicators. The coefficient  $\beta_{32}$  represents the effect of PMSB at the end of the intervention (6-months), while  $\beta_{33}$  represents the effect of PMSB six-months post-intervention (12-months).

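### The primary spline model is written with its knot on the wrong time scale, and the printed 12-month formula is not a treatment effect

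*Combined protocol and SAP*

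**What the plan says.** All of this is in the Analytical methods section of the combined protocol and SAP. Time "equals to -4 for 2-month follow-up, 0 for 6-month follow up, and 6 for 12-month follow-up". The knot t* is defined as a calendar month, "to be the month when the intervention stopped, i.e., 6 months after baseline", and the purpose is clear: "our primary analysis employed linear spline models to divide the time axis into two segments". The text defines a plus-function that is zero up to the knot, but equations (1) and (2) print (Time - t*) without the plus sign.

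The interpretation that follows reads β1 as the 6-month effect and β5 as the between-arm difference in the post-intervention trend. It reads the constant at month 6 with both Time = 0 and (Time - t*) = 0. The 12-month effect is described as coming from the time-by-intervention interactions. The closing sentence then takes Time = 6 and t* = 6 together and concludes that "since PMSB lasted six months, the intervention effect evaluated 12 months after baseline is given by" β1 + 6β2 + 6β3.

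**The concern.** Time and t* have to be on one scale, and they are not. Month 6 is 0 on the centred scale, so a knot at 6 falls on the last visit and leaves no second segment. If the code did this, the test of β5 does not exist and β1 no longer estimates the 6-month effect. The global test of the β1 terms in equation (2) would then not address month 6 either.

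The 12-month formula is a separate error. In equation (1) β2 multiplies Time alone and is common to both arms, so it has no place in a treatment-minus-control contrast. Used as printed, the formula moves the control arm's own time trend into the treatment effect. It also leaves out β5, the term that lets the effect fade or grow after the intervention ends, which is the reason given for choosing a spline. Software will usually flag a rank-deficient design. It will not flag a wrong linear combination, which simply returns a plausible number.

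**Working it through.** **Inputs.** Time = -4, 0, 6. Fixed effects in equation (1), apart from the baseline covariate: intercept, β1 (arm), β2 (Time), β3 (arm × Time), β4 (spline), β5 (arm × spline). Two arms and three visits give six cell means for six coefficients.

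**Step 1: rank of the design under each reading.**

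| Reading | Spline column at months 2, 6, 12 | Rank | 12-month contrast |
|---|---|---|---|
| plus-function, knot 6 | 0, 0, 0 | 4 of 6 | β1 + 6β3 |
| no plus, knot 6 | -10, -6, 0 | 4 of 6 | β1 + 6β3 |
| plus-function, knot 0 | 0, 0, 6 | 6 of 6 | β1 + 6β3 + 6β5 |
| no plus, knot 0 | -4, 0, 6 | 4 of 6 | β1 + 6β3 + 6β5 |

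Uncentred Time (2, 6, 12) with a knot of 6 also has rank 6, but the 6-month effect is then β1 + 6β3 and the 12-month effect β1 + 12β3 + 6β5. The coefficient of β2 is zero under all five readings, so the plan's β1 + 6β2 + 6β3 cannot be reproduced under any of them.

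**Step 2: the correct contrast.** Let d2, d6 and d12 be the arm differences at months 2, 6 and 12. With the knot at 0:

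- d6 = β1
- d2 = β1 - 4β3, so β3 = (d6 - d2)/4
- d12 = β1 + 6β3 + 6β5, so β5 = (d12 - d6)/6 - β3

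The printed formula minus the correct one is 6β2 - 6β5 = 6 × (β2 - β5), which is zero only if β2 = β5.

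**Step 3: size of the 12-month error, if the printed formula was coded.** The printed value equals d6 + 1.5 × (d6 - d2) + 6β2. The effects below are assumptions in SD units, positive = benefit. The control arm is assumed to change by -0.1 to +0.1 SD from month 2 to 6, so β2 = -0.025 to +0.025 and 6β2 = -0.15 to +0.15.

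| d2 / d6 / d12 | Correct | Printed formula |
|---|---|---|
| 0 / 0 / 0 | 0 | -0.15 to +0.15 |
| 0.4 / 0.4 / 0.4 | 0.40 | 0.25 to 0.55 |
| 0.4 / 0.4 / 0.6 | 0.60 | 0.25 to 0.55 |
| 0.1 / 0.4 / 0.2 | 0.20 | 0.85 ± 0.15 = 0.70 to 1.00 |

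**Step 4: size of the 6-month error, if the knot was coded as 6.** Each arm then has one straight line. The imputed datasets are balanced over visits, "each one consisting of 307 participants with three follow-up assessments per participant", and the model has random intercepts only. The straight-line estimate at Time = 0 therefore gives visit i the weight 1/3 + (0 - m)(Ti - m)/SS, where m = 2/3 and SS = (196 + 4 + 256)/9 = 50.67. The weights are 0.395, 0.342 and 0.263 for months 2, 6 and 12. Against an assumed 6-month effect of 0.40:

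- 0.1 / 0.4 / 0.2 gives 0.23 (-43%)
- 0.2 / 0.4 / 0.4 gives 0.32 (-20%)
- 0.4 / 0.4 / 0.4 and the linear 0.3 / 0.4 / 0.55 give 0.40 (no bias)
- 0.4 / 0.4 / 0.6 gives 0.45 (+13%)
- 0.5 / 0.4 / 0.5 gives 0.47 (+16%)

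**Step 5: simulation check.** One dataset of 20,000 participants was fitted with a random-intercept model, with true effects 0.1 / 0.4 / 0.2 and control means 0 / 0.1 / 0.15. The straight-line β1 was 0.235 and the spline β1 was 0.401. The corrected 12-month effect was 0.198 and the printed formula gave 0.990. With no true effect at any visit, the corrected value was -0.012 and the printed one 0.161.

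**The case against.** The best defence is that both faults are slips of notation. Nearly all the surrounding text needs a knot at month 6: two segments, t* given as a calendar month, the spline term equal to zero at month 6, and β5 interpreted as estimable. The single clause with t* = 6 reads naturally as a month label left on the uncentred scale. Equation (1) has exactly two time-by-intervention interactions, β3 and β5, and the printed formula has exactly two terms multiplied by 6, so the subscripts may simply be wrong. The analyses are reported in the past tense, the 6-month effect is unaffected on the intended reading, and equation (3) gives visit-specific effects without a knot.

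Much of this stands. A subscript slip is the likeliest explanation, and the documents do not show that any estimate is wrong. Leaving out β5 is an error only once the knot works. None of this makes the written model correct: β2 is wrong under every reading, and the text cannot be followed as it stands to reproduce the primary model or its 12-month effect.

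Equation (3) is only a partial safeguard. It is a sensitivity analysis and treats baseline as an outcome, whereas equation (1) adjusts for it. Assuming equal arms and a baseline correlation of 0.5, chance imbalance alone separates the two estimates by an SD of about 0.5 × 2/√307 = 0.06. That is similar to the smaller biases in Step 4.

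**Conclusion.** The concern holds as an error in the written specification of the primary model, and it must be corrected. The algebra in Steps 1 and 2 needs no assumption. The sizes are conditional twice over: on the code having followed the text, and on visit effects and control-arm trends that the documents do not give. Under those assumptions the 12-month error ranges from modest to several times the true effect. The 6-month error runs from -43% to +16% and is zero when the effect is constant or linear in time. The direction of either error depends on the trajectories.

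**What to change.** - Define Time as months since baseline minus 6. The present wording, months between successive assessments, does not match the coding -4, 0, 6.
- State t* = 0 on that scale, so that the spline term is 0, 0, 6 at months 2, 6 and 12, and print the plus-function in equations (1) and (2).
- Replace the 12-month effect with β1 + 6β3 + 6β5.
- Check the code for both the knot and the 12-month contrast.
- Compare the 6- and 12-month effects with β32 and β33 from equation (3), expecting small differences from the handling of baseline. A sharper check is to fit visit indicators to the three follow-ups with baseline as a covariate: with three visits the working spline is saturated, so the visit effects should agree.

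The cost is some SAP wording, two equations, one formula and a code check. A re-run is needed only if the code followed the text on either point.
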